7.6 Adverse Events of Special Interest

In this study, the following adverse events are to be reported to BMS, regardless of whether these reports are classified as serious or unexpected:

- Potential or suspected cases of liver injury including but not limited to liver test abnormalities, jaundice, hepatitis or cholestasis.

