5 TREATMENT AND/OR IMAGING PLAN

5.1 Treatment Regimen

Patients eligible for the study will receive the standard of care and FDA approved dosing of apixaban. Platelet count recovery in patients with HIT is typically 5-7 days. Warkentin demonstrated that patients with isolated HIT (HIT without thrombosis) have an increased risk of thrombosis for up to 30 days after diagnosis.⁴ Therefore, for patients with isolated HIT (HIT without thrombosis), patients will receive apixaban, 10 mg twice a day for 7 days followed by 5 mg twice a day for 23 days, for a total of 30 days of apixaban dosing. For patients with HITT, patients will receive apixaban, 10 mg twice a day for 7 days followed by 5 mg twice a day for 83 days, for a total of 90 days of apixaban dosing, which are the current CHEST guidelines for duration of treatment for patients with provoked VTE.²⁴ The proposed apixaban dosing regimen is taken from the current FDA approved dosing schedule for the treatment of venous thromboembolism [VTE] with apixaban which is 10 mg twice daily for 7 days followed by 5 mg twice daily thereafter.

Treatment will initially be administered on an inpatient basis but once patient is medically cleared to be discharged, the remaining treatment will be administered on an outpatient basis. Reported adverse events and potential risks are described in Section 7. Appropriate dose modifications are described in Section 6. No investigational or commercial agents or therapies other than those described below may be administered with the intent to treat the participant.

Regimen Description					
Agent	Premedications; Precautions	Dose	Route	Schedule*	Length of treatment
Apixaban	No premedications required	10 mg twice a day	Oral	For the first 7 days**	1 month (30 days) total for HIT patients and 3 months (90 days) total for HITT patients
Apixaban	No premedications required	5 mg twice a day	Oral	To start this dose after patient completes the first 7 days with the 10 mg twice a day dose.**	

* This is the FDA approved dose for apixaban for prevention and treatment of venous thromboembolism.
 
** Patients will not start the 5 mg dose prior to 7 days as this is the FDA approved dosing structure.
					

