- Blood coagulation profile: Activated partial thromboplastin time (aPTT), prothrombin time/international normalized ratio (PT/INR).
- Serum Chemistries: creatinine, BUN, Na, K, CO₂ and glucose.
- Hepatic Profile: total bilirubin, AST, ALT.

5.3.2 **Imaging (Day -7 to Day +3)**

- As part of standard of care, all patients with confirmed HIT or high suspicion of HIT undergo bilateral lower extremity non invasive testing to rule out deep vein thrombosis. LENI is not required if the patient is diagnosed with a Pulmonary Embolism.
- This can occur anytime from Day -7 to Day +3. Only one test is required.

5.3.3 **Initiation of Therapy: Day 1**

Once the patient has been consented and is determined to meet inclusion/exclusion criteria as described above in Section 3.1 and 3.2, the following study procedures will be performed. These assessments do not need to be repeated if Screening was conducted on D1.

- Physical Exam
- Clinical Assessment for signs and symptoms of TEC and any significant findings
- Vital signs
- Weight
- ECOG
- Laboratory tests:
 - CBC: hemoglobin, hematocrit, WBC with differential, and platelet count
 - Chemistries: creatinine, BUN, Na, K, CO₂ and glucose
 - Hepatic panel: total bilirubin, AST, ALT
 - Coagulation profile: aPTT, PT/INR
- Record Concomitant Medications
- Assess and Record Adverse Events
- Initiation of Therapy: dispense study medication and diary
 - Administer study medication: Apixaban
 - Initiate daily oral therapy at 10 mg twice daily for 7 days followed by 5 mg twice daily thereafter.

5.3.4 **Hospital Course: Day 2 - Day of Discharge:**

The following procedures will be done on a daily basis until discharge from the hospital:

- Clinical Assessment for signs and symptoms of thromboembolic complications and any significant findings.
- Vital signs
- Laboratory Tests:
 - CBC: hemoglobin, hematocrit, WBC with differential, and platelet count
 - Chemistry Panel: creatinine, BUN, Na, K, CO2 and glucose
- Assess and record Adverse Events
- Record Concomitant Medications
- Record all doses of administered Apixaban (from the day it was initiated).

Before discharge, ensure enough study medication is dispensed to last at least until the 30 Day Follow Up visit (for HIT) or the 90 Day Follow Up visit (for HITT).

5.3.5 **Follow-up: Day 30 (+/- 5 days)**

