The patient will be assessed on Day 30 (\pm 5 days) from initiation of therapy, preferably in clinic. If clinic follow up is feasible, all of the following data must be recorded. If patient is unable to come to clinic (ie due to living in another city or unable to travel), day 30 follow up can be completed by telephone interview and the labs, exam and vitals will not be recorded.

The following data must be recorded:

- Summary of patient's clinical course
- Any adverse events that occurred between Day of Discharge through Day 30 including signs and symptoms of TEC.
- CBC, chemistries, coagulation profile*
- Physical exam and vital signs*
- Concomitant Medications
- For patients discharged on apixaban:
 - Retrieve study medication and diary
 - Record the stop date of discontinuation of apixaban.

**unable to obtain if follow up is telephone interview*

5.3.6 **Follow-up for patients with HITT: Day 90 (+/- 5 days)**

The patient will be assessed on Day 90 (± 5 days), from initiation of therapy, preferably in clinic. If clinic follow up is feasible, all of the following data must be recorded. If patient is unable to come to clinic (ie due to living in another city or unable to travel), day 90 follow up can be completed by telephone interview and the labs, exam and vitals will not be recorded.

The following data must be recorded:

- Summary of patient's clinical course
- Any adverse events that occurred between Day of Discharge through Day 90 including signs and symptoms of TEC.
- CBC, chemistries, coagulation profile*
- Physical exam and vital signs*
- Concomitant Medications
- For patients discharged on apixaban:
 - Retrieve study medication and diary
 - Record the stop date of discontinuation of apixaban.

**unable to obtain if follow up is telephone interview*

5.3.7 **Follow-up 30 days after last dose of therapy (+/- 5 days)**

The patient will be assessed on 30 days (± 5 days), after last dose of therapy. If clinic follow up is feasible, all of the following data must be recorded. If patient is unable to come to clinic (ie due to living in another city or unable to travel), this follow up can be completed by telephone interview and the labs, exam and vitals will not be recorded.

The following data must be recorded:

- Summary of patient's clinical course
- Any adverse events through 30 days after the last dose of therapy including signs and symptoms of TEC.
- CBC, chemistries*
- Physical exam and vital signs*
- Concomitant Medications

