7.3 Serious Adverse Event

A Serious Adverse Event (SAE) is any untoward medical occurrence that at any dose:

- results in death
- is life-threatening (defined as an event in which the participant was at risk of death at the time of the event; it does not refer to an event which hypothetically might have caused death if it were more severe)
- requires inpatient hospitalization or causes prolongation of existing hospitalization (see **NOTE** below)
- results in persistent or significant disability/incapacity
- is a congenital anomaly/birth defect
- is an important medical event (defined as a medical event(s) that may not be immediately life-threatening or result in death or hospitalization but, based upon appropriate medical and scientific judgment, may jeopardize the subject or may require intervention [eg, medical, surgical] to prevent one of the other serious outcomes listed in the definition above.) Examples of such events include, but are not limited to, intensive treatment in an emergency room or at home for allergic bronchospasm; blood dyscrasias or convulsions that do not result in hospitalization.)
- Suspected transmission of an infectious agent (eg, pathogenic or nonpathogenic) via the study drug is an SAE.

Although pregnancy, overdose, potential drug-induced liver injury (DILI) and cancer are not always serious by regulatory definition, these events must be handled as SAEs.

Any component of a study endpoint that is considered related to study therapy should be reported as an SAE if it meets the above SAE definition (eg, death is an endpoint, if death occurred due to anaphylaxis, anaphylaxis must be reported).

NOTE: The following hospitalizations are not considered SAEs:

- a visit to the emergency room or other hospital department < 24 hours, that does not result in admission (unless considered an important medical or life-threatening event)
- elective surgery, planned prior to signing consent
- admissions as per protocol for a planned medical/surgical procedure
- routine health assessment requiring admission for baseline/trending of health status (eg, routine colonoscopy)
- Medical/surgical admission other than to remedy ill health and planned prior to entry into the study. Appropriate documentation is required in these cases

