8.2 Pharmacodynamics

As a result of FXa inhibition, apixaban prolongs clotting tests such as prothrombin time (PT), INR, and activated partial thromboplastin time (aPTT). Changes observed in these clotting tests at the expected therapeutic dose, however, are small, subject to a high degree of variability, and not useful in monitoring the anticoagulation effect of apixaban.

The Rotachrom® Heparin chromogenic assay was used to measure the effect of apixaban on FXa activity in humans during the apixaban development program. A concentration dependent increase in anti-FXa activity was observed in the dose range tested and was similar in healthy subjects and patients with AF. This test is not recommended for assessing the anticoagulant effect of apixaban.

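### No liver test is scheduled after the first apixaban dose, although liver injury is the only adverse event of special interest, so symptomless abnormalities will not be found systematically

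*Combined protocol and SAP*

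**What the plan says.** Section 7.6 lists one adverse event of special interest, to be reported to the drug supplier whether or not it is serious or unexpected: "Potential or suspected cases of liver injury including but not limited to liver test abnormalities, jaundice, hepatitis or cholestasis". Section 7.3 adds: "Although pregnancy, overdose, potential drug-induced liver injury (DILI) and cancer are not always serious by regulatory definition, these events must be handled as SAEs". The introduction to section 7 says an abnormal laboratory value is not normally an adverse event, but makes an exception for a value that meets the SAE or special-interest definition.

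Treatment lasts "1 month (30 days) total for HIT patients and 3 months (90 days) total for HITT patients" (5.1). The screening bloods include "Hepatic Profile: total bilirubin, AST, ALT" (5.3.1), and Day 1 repeats that panel unless screening took place the same day (5.3.3). From Day 2 to discharge the daily bloods are a blood count and "Chemistry Panel: creatinine, BUN, Na, K, CO2 and glucose" (5.3.4). At Day 30 and Day 90 they are "CBC, chemistries, coagulation profile" (5.3.5, 5.3.6). The visit 30 days after the last dose has a blood count and chemistries only (5.3.7).

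**The concern.** The plan makes liver-test abnormalities reportable in their own right, and then schedules no test that could show one once treatment has begun. Section 3.1.7 admits patients with AST and ALT up to 2.5 times the upper limit of normal, so some may start with raised values and have no scheduled later value for comparison.

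What is at stake is how the safety report can be read. If few or no liver events are reported, a reader cannot tell whether livers were unaffected or were not tested. Because 7.3 treats potential drug-induced liver injury as an SAE, a symptomless case that is never tested for is also an SAE that is never reported. The primary endpoint, the sample size and the stopping rules do not depend on any of this.

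**Working it through.** The plan gives no figure to reproduce. The check sets the procedure text beside the calendar in section 10, visit by visit.

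| Visit | Section | AST, ALT, bilirubin in the procedure text? | Hepatic row marked in the calendar? |
|---|---|---|---|
| Screening | 5.3.1 | Yes | Yes |
| Day 1 | 5.3.3 | Yes, unless screened that day | Yes |
| Day 2 to discharge, daily | 5.3.4 | No | No |
| Day 30 | 5.3.5 | No | No |
| Day 90 (HITT) | 5.3.6 | No | No |
| 30 days after last dose | 5.3.7 | No | No |
| Unscheduled | 5.3.8 | Yes, conditional | Yes |

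1. *Could chemistries include liver tests?* No. Section 5.3.4 and calendar footnote 3 both define the chemistry panel as creatinine, BUN, sodium, potassium, CO2 and glucose. The hepatic profile is a separate row with its own footnote.

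2. *Is the Day 1 panel an on-treatment value?* No. The calendar requires these assessments before any study drug, and 5.2 uses the Day 1 AST and ALT to reconfirm eligibility.

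3. *Could the table extraction have lost calendar marks?* This is unlikely to matter, because the procedure text gives the same answer for every visit without relying on the calendar.

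4. *Count of scheduled panels.* Before the first dose: 2, or 1 if screening is on Day 1. After the first dose: 0 over 30 days (isolated HIT), 0 over 90 days (HITT) and 0 at the post-treatment visit.

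5. *Do other provisions fill the gap?*
   - 5.3.8 specifies a panel only for visits between discharge and Day 30 (or Day 90 for HITT) that are HIT-related and lead to hospitalization and treatment, and only where feasible. It does not cover the initial inpatient stay or the period after treatment, and an isolated liver problem would not qualify.
   - 7.5 requires significant worsening on any safety assessment to be recorded, including assessments outside the protocol. It orders no test.
   - Adverse events are elicited by open questions, spontaneous report or examination, and patients are not to be asked about particular events (section 7). That can reveal jaundice but not a silent rise in enzymes. A telephone follow-up also removes the examination and the bloods.

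6. *Treatment time involved.* Assume the 1/4 HITT and 3/4 isolated HIT mix that section 13.1 takes from its real-world source, with full courses for all 49 patients. Then 49 × 3/4 ≈ 37 and 49 × 1/4 ≈ 12, which gives 37 × 30 + 12 × 90 = 1,110 + 1,080 = 2,190 planned patient-days. This is an upper figure, because patients whose confirmatory test is negative stop therapy (5.7). Counting only the 44 expected confirmed patients gives 33 × 30 + 11 × 90 = 990 + 990 = 1,980, still assuming full courses. The zero count in step 4 depends on neither figure.

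**The case against.** The strongest reply is that 7.6 is a reporting duty and not a measurement aim. It says which cases go to the supplier once they come to light. Liver outcomes are not among the objectives in 1.2 and 1.3, are not named among the monitored events in 11.1.2, and have no planned analysis. The apixaban reactions in 7.7 are listed down to a frequency of 0.1% and include no hepatic event, although that section refers to the prescribing information for the complete list. At an assumed rate of 0.1%, 49 patients would yield 49 × 0.001 ≈ 0.05 cases. Even with every patient tested and none abnormal, the upper limit of an exact 90% interval, the plan's own convention, would be 1 − 0.05^(1/49) ≈ 5.9%. The trial can say little about rare liver injury whatever is scheduled.

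This stands as an argument about severity: no estimand, threshold or stopping rule is affected. It does not remove the gap. The plan counts laboratory abnormalities within its special-interest event, does not say that detection is passive, and already draws blood at the visits in question.

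A reader might go further and infer that on-treatment liver abnormalities will go undetected altogether. The documents do not support that. The conditional panel in 5.3.8, the recording rule in 7.5, examinations at clinic visits, and adverse-event collection to at least 30 days after the last dose (7.1.1) are all routes by which a case could surface. All patients also start as inpatients, so liver tests ordered for clinical reasons are plausible.

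**Conclusion.** The point holds in limited form. Liver injury, including laboratory abnormalities, is the sole adverse event of special interest, and the plan schedules 0 liver panels after the first dose in either group. Symptomless abnormalities will not be detected systematically, no on-treatment rate can be estimated, and an absence of reported liver events could reflect an absence of testing. The finding rests on the procedure text and the calendar, which agree, and on no statistical assumption.

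Two further inferences should be avoided. The 1,980 to 2,190 patient-days describe planned exposure under full courses; they do not estimate missed events. Nor does the statement in 8.2 that clotting tests are "not useful in monitoring the anticoagulation effect of apixaban" show that the Day 30 and Day 90 coagulation profile is dispensable. It concerns only apixaban's anticoagulant effect, and 11.1.2 also monitors for disseminated intravascular coagulopathy.

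This is an inexpensive improvement to safety ascertainment that should be made. It is not a flaw in the primary analysis.

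**What to change.** In the calendar and in 5.3.4 to 5.3.7, add the hepatic profile (total bilirubin, AST, ALT) to one in-hospital draw after dosing starts, for example the last before discharge, and to the existing in-clinic draws at Day 30, Day 90 (HITT) and 30 days after the last dose. A patient seen in clinic throughout would then have 1 + 1 + 1 = 3 panels after the first dose with isolated HIT, and 1 + 1 + 1 + 1 = 4 with HITT, instead of 0.

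Summarise change from the Day 1 value (or screening, if Day 1 was not repeated) descriptively in the full analysis set, with the number of patients actually tested at each visit. Keep the coagulation profile. If the sponsor prefers not to add tests, 7.6 and the calendar should still be reconciled by stating that liver events are detected passively, and the report should say so.

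The cost is a protocol amendment and a small assay charge on blood already drawn, with no extra visit or venepuncture. Patients followed by telephone would still lack the later panels, so the in-hospital draw may be their only value after dosing starts. No dose or treatment rule changes.

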7.7 Expected Toxicities

7.7.1 Adverse Events List for Apixaban

The safety of APIXABAN has been evaluated in non HIT or non HITT venous thromboembolism patient populations in the AMPLIFY and AMPLIFY-EXT studies, including 2676 patients exposed to APIXABAN 10 mg twice daily, 3359 patients exposed to APIXABAN 5 mg twice daily, and 840 patients exposed to APIXABAN 2.5 mg twice daily.

Common adverse reactions ($\geq 1\%$) were gingival bleeding, epistaxis, contusion, hematuria, rectal hemorrhage, hematoma, menorrhagia, and hemoptysis.

AMPLIFY Study

The mean duration of exposure to APIXABAN was 154 days and to enoxaparin/warfarin was 152 days in the AMPLIFY study. Adverse reactions related to bleeding occurred in 417 (15.6%) APIXABAN-treated patients compared to 661 (24.6%) enoxaparin/warfarin treated patients. The discontinuation rate due to bleeding events was 0.7% in the APIXABAN-treated patients compared to 1.7% in enoxaparin/warfarin-treated patients in the AMPLIFY study.

In the AMPLIFY study, APIXABAN was statistically superior to enoxaparin/warfarin in the primary safety endpoint of major bleeding (relative risk 0.31, 95% CI [0.17, 0.55], P-value <0.0001).

Adverse reactions occurring in 1-3% of patients in the AMPLIFY study include: epistaxis, contusion, hematuria, menorrhagia, hematoma, hemoptysis, rectal hemorrhage, gingival bleeding.

AMPLIFY-EXT Study

The mean duration of exposure to APIXABAN was approximately 330 days and to placebo was 312 days in the AMPLIFY-EXT study. Adverse reactions related to bleeding occurred in 219 (13.3%) APIXABAN-treated patients compared to 72 (8.7%) placebo-treated patients. The discontinuation rate due to bleeding events was approximately 1% in the APIXABAN-treated patients compared to 0.4% in those patients in the placebo group in the AMPLIFY-EXT study.

Adverse reactions occurring in 1-2% of patients in the AMPLIFY-EXT study include: epistaxis, contusion, hematuria, hematoma, gingival bleeding.

Other Adverse Reactions

Less common adverse reactions in APIXABAN-treated patients in the AMPLIFY or AMPLIFYEXT studies occurring at a frequency of $\geq 0.1\%$ to $< 1\%$:

Blood and lymphatic system disorders: hemorrhagic anemia

Gastrointestinal disorders: hematochezia, hemorrhoidal hemorrhage, gastrointestinal hemorrhage, hematemesis, melena, anal hemorrhage

Injury, poisoning, and procedural complications: wound hemorrhage, postprocedural hemorrhage, traumatic hematoma, periorbital hematoma

Musculoskeletal and connective tissue disorders: muscle hemorrhage

Reproductive system and breast disorders: vaginal hemorrhage, metrorrhagia, menometrorrhagia, genital hemorrhage

Vascular disorders: hemorrhage

Skin and subcutaneous tissue disorders: ecchymosis, skin hemorrhage, petechiae

Eye disorders: conjunctival hemorrhage, retinal hemorrhage, eye hemorrhage

Investigations: blood urine present, occult blood positive, occult blood, red blood cells urine positive

General disorders and administration-site conditions: injection-site hematoma, vessel puncture-site hematoma

Please refer to the approved apixaban U.S prescribing information for a complete listing of adverse events

7.8 Adverse Event Characteristics

- **CTCAE term (AE description) and grade:** The descriptions and grading scales found

in the revised NCI Common Terminology Criteria for Adverse Events (CTCAE) version 4.0 will be utilized for AE reporting. All appropriate treatment areas should have access to a copy of the CTCAE version 4.0. A copy of the CTCAE version 4.0 can be downloaded from the CTEP web site

http://ctep.cancer.gov/protocolDevelopment/electronic_applications/ctc.htm.

- **For expedited reporting purposes only:**
 - AEs for the agent(s) that are listed above should be reported only if the adverse event varies in nature, intensity or frequency from the expected toxicity information which is provided.
 - Other AEs for the protocol that do not require expedited reporting are outlined in the next section (Expedited Adverse Event Reporting) under the sub-heading of Protocol-Specific Expedited Adverse Event Reporting Exclusions.
- **Attribution of the AE:**
 - Definite – The AE *is clearly related* to the study treatment.
 - Probable – The AE *is likely related* to the study treatment.
 - Possible – The AE *may be related* to the study treatment.
 - Unlikely – The AE *is doubtfully related* to the study treatment.
 - Unrelated – The AE *is clearly NOT related* to the study treatment.

7.9 Expedited Adverse Event Reporting

7.9.1 In the event of an unanticipated problem or life-threatening complications treating investigators must immediately notify the Overall PI.

7.9.2 Investigators **must** report to the Overall PI any serious adverse event (SAE) that occurs after the initial dose of study treatment, during treatment, and within 30 days after the last dose of treatment.

